6.0 MEASUREMENT OF EFFECT

All scales being used in this study have good psychometric properties with similar populations. Listed below are the factors to be measured and measurement instruments with references to validation studies.

Quantitative analyses. Two types of analyses are planned: 1) a general, whole-sample analysis of outcomes not specific to any condition, and 2) analyses of condition-specific outcomes that permit integration across condition categories.

The first, general outcome category includes quality of life and primary care use which will be assessed with the same measures and same metrics regardless of conditions.

The second type of analysis is for condition-specific outcomes: mm Hg for hypertension, mg/dL for hyperlipidemia, HbA1c for diabetes, and pain for arthritis. These outcomes will be analyzed in 2 ways. In one approach, scores on each measure will be transformed to Z scores and combined to create the composite score across all 5 outcomes, which will constitute an improper linear model with unit weighting; this is a secondary outcome. Thus, patients will be compared based on the pooled composite. Because we believe that change in the composite will reflect specific conditions and combinations, these factors will be entered as covariates in separate analyses to determine whether particular conditions or combinations of conditions are significantly related to the magnitude of treatment effects on the composite. Because patients often have more than 3 chronic conditions, we will code for the presence or absence of other common chronic conditions (e.g., cancer, pain, depression, anxiety, falls, heart disease, diabetes, and osteoporosis). The particular combinations involved will be entered as dummy variables. The second approach to the analyses of condition-specific outcomes will involve examining condition-specific outcomes individually, with only those individuals in the C-CHESS and comparison groups who have the pertinent diagnosis contributing data to the analysis (e.g., only those with diabetes will contribute data to the analyses involving HbA1c). The analytic approach to symptoms would be similar to the approach to the condition-specific tests. We will set a threshold for inclusion in the composite, and use as individual dependent variables the symptoms that occur in $\geq 10\%$ of the sample.

This analysis plan should allow us to examine treatment-related change with regard to: 1) condition-specific clinical outcomes; 2) general outcomes reflecting disease coping and burden; and 3) condition-specific clinical outcomes when modeled as a composite score that reflects status with regard to the 5 major conditions.

Effectiveness of TAU+Internet vs. TAU+C-CHESS. We will use separate mixed-effects models to evaluate the primary and secondary outcomes. Each model will include fixed effects for TAU+Internet vs. TAU+C-CHESS, time (6, 12, and 18 months), and the arm-by-time interaction, including the baseline assessment of each outcome as a covariate. We will also determine whether clinic exerts main effects or interacts with the treatment condition. The latter will test the consistency of C-CHESS effects over different clinics and whether data can be pooled across sites. The initial intercepts will be modeled as random variables to estimate variance and covariance of intervention effects at the different fixed occasions, and across and between patients. These models account for dependence among successive observations made on the same patient and use all available data (not just complete cases). We will conduct treatment time contrasts between and within groups to test time-based effects, with our primary analysis focused on the C-CHESS effect at 12 months. Generalized linear mixed-effects models will be used for the count outcomes addressing primary care use. If a count outcome has sufficient variability, Poisson regression will be used; if not, the outcome will be coded as dichotomous (some service use vs. none) and logistic regression will be used.

Mediation. We will test 4 potential mediators of the intervention's effect on the primary and secondary outcomes. We will also test whether the condition-specific and composite secondary outcomes mediate the intervention's effect on the primary outcomes. Mediation will be tested by individually testing the 2 paths in the indirect effect and will conclude statistical significance only when the null hypothesis of no effect is rejected for both paths in the mediational pathway. To limit the number of analyses, we will use Bolt's approach⁹⁴ of first using a screening approach that examines only mediational models with outcomes and potential mediators significantly affected by the intervention. We will then use separate univariate models to determine which mediate the intervention effect on given outcomes. If 2 or 3 mediators are found, we will simultaneously enter all the significant mediators into the same model. If 4 mediators are found, we will enter the 'strongest' mediator first and then test whether adding remaining mediators shows significant mediational effects.

Moderation. A moderation model holds that the strength of the relation between intervention and outcomes is a function of the level of other variables and tries to explain under what conditions the treatment model functions. We will test whether gender, age (65-74 vs ≥ 75), and number of chronic conditions (3, 4, or 5) moderate the effect of the intervention on outcomes. Also, when standardized composites are used as the dependent variable, type of chronic condition will be used as a moderator to determine if the composite varies meaningfully by condition. Participants will list changes in chronic conditions at 6 and 12 months.

Moderated mediation. Although both constructs of mediation and moderation are of interest in our research, the process is more complex than just these factors. For example, a variable (e.g., relatedness) may act as a stronger mediator for 1 subgroup (e.g., women) than another (e.g., men).

Qualitative analyses. Through 3 interviews we will gather qualitative data from clinic staff to provide additional insights into their use of the CR.

In the baseline interview, clinicians will be asked about anticipated barriers to participation and concerns about navigating C-CHESS and incorporating it into their treatment plans. Near the end of a clinic's intervention period, clinicians will be asked about factors that influenced their use of C-CHESS, perceptions of short- and long-term effects, and ways in which similar clinics might implement and sustain C-CHESS. In the post-test period, clinicians will be asked about enduring effects observed and implications of losing C-CHESS for treating their patients.

Feedback from these interviews will be used anecdotally and will help the research team improve the design and delivery of the CR.

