Elder Tree was tested in an RCT involving 399 older adults from 3 Wisconsin counties (urban, rural, and suburban). We followed participants for 18 months and assessed outcomes at 0, 6, 12, and 18 months.⁴¹

Elder Tree subjects were asked to identify their chronic conditions so we could examine data about the impact of Elder Tree on those with MCCs. We identified 66 older adults with at least 3 of the 4 target MCCs. Subjects' conditions included (in addition to hypertension, hyperlipidemia, diabetes, and arthritis) cancer, pain, depression, anxiety, heart disease, obesity, osteoporosis, and falls. The Elder Tree RCT included 4 measures we plan to use in this study: health-related quality of life, use of primary care services, relatedness (feeling connected with others), and number of symptoms. For the clusters we propose to study in this project, we found moderate (0.4+) to large effect sizes, all favoring Elder Tree, with 2 exceptions in which small effects favored Elder Tree. These data helped us conduct power analyses and estimate sample sizes for the C-CHESS RCT.

Effect sizes from Elder Tree data					
Chronic Condition Clusters	n Control/ Elder Tree	Quality of Life	Fewer Primary Care Visits	Relatedness	Fewer Symptoms
Hypertension/hyper-lipidemia/arthritis	17/21	0.20	0.61	0.56	0.56
Hypertension/hyper-lipidemia/diabetes	11/10	0.40	0.66	0.36	0.45
Hypertension/arthritis/diabetes	16/11	0.96	0.71	0.52	0.53
Hyperlipidemia/arthritis/diabetes	14/14	1.09	0.56	0.91	0.75

As mentioned above, C-CHESS will add to Elder Tree the Clinician Report (CR), which alerts clinicians when thresholds are reached in a patient's status. We used a similar system in a lung cancer RCT comparing CHESS to CHESS+CR. The addition of the CR to CHESS improved ($p < .001$) symptom distress by over 100% (26.2% improvement with CHESS vs. 53% in those with CHESS+CR; $n = 71$ vs. 68 respectively). These statistics are averaged across 6 observations over 12 months. We expect the proposed CR to increase the effects of C-CHESS compared with Elder Tree.

Innovation: The intervention is innovative for the following reasons.

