1.0 STUDY OBJECTIVES

This project will test the use of an eHealth intervention called C-CHESS, to modify health behaviors and improve health outcomes in older adults with comorbid chronic diseases and health conditions.

Aim 1 Refine C-CHESS, using feedback from patients and primary care clinicians.

Aim 2 Conduct a randomized clinical trial to test 4 hypotheses:

1. *Primary outcomes:* Patients assigned to TAU+C-CHESS will have better quality of life and less primary care use (fewer visits) than those assigned to TAU+Internet.
2. *Secondary outcomes:* Patients assigned to TAU+C-CHESS will have improved composite scores; improved individual condition outcomes (mm Hg for hypertension, mg/dL for hyperlipidemia (LDL), HbA1c for diabetes, and pain for arthritis); and fewer symptoms from a list than patients assigned to TAU+Internet.
3. *Mediators:* Patients assigned to TAU+C-CHESS will have, compared with patients assigned to TAU+Internet, greater adherence to medications and appointments as well as improved competence,

relatedness, and autonomy.

4. *Moderators:* Improvements in primary outcomes for TAU+C-CHESS vs. TAU+Internet will be greater for women than men, those ≥ 75 vs. 65 to 74, and those with 3-5 chronic conditions vs. 6+.

Aim 3 Analyze data from the RCT and publish results.

Exploratory questions:

- Does C-CHESS reach a large proportion of targeted patients, get a large proportion of targeted clinicians to use C-CHESS, get a large proportion of patients to regularly use C-CHESS, and maintain that performance over time)?
- Does the use of specific C-CHESS services affect outcomes?
- Does the use of C-CHESS affect other health service use?

Primary Aim

Patients assigned to TAU+C-CHESS will have better quality of life and fewer primary care visits than those assigned to TAU+Internet.

C-CHESS will contain the Clinician Report to make it easier for PCPs to respond to important patient changes, pilot data suggested that primary care visits could be reduced. Reducing the number of primary care visits will both lessen provider burden and ultimately reduce healthcare costs.

Secondary Aim

Patients assigned to TAU+C-CHESS will have improved composite scores; improved individual condition outcomes (mm Hg for hypertension, mg/dL for hyperlipidemia (LDL), HbA1c for diabetes, and pain for arthritis); and fewer symptoms from a list than patients assigned to TAU+Internet.

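### The secondary hypothesis concerns the number of symptoms, but section 6.0 specifies an undefined composite and symptom-by-symptom tests, with no visit fixed for the 10% rule and no error control

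*Combined protocol and SAP*

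**What the plan says.** Section 1.0 (Aim 2, second hypothesis, repeated under Secondary Aim) predicts "fewer symptoms from a list than patients assigned to TAU+Internet". The Preliminary data section lists four Elder Tree measures to be carried into this trial, ending with "relatedness (feeling connected with others), and number of symptoms". The quantity at issue is therefore a count.

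The only symptom-specific analysis text is at the end of the discussion of condition-specific outcomes in section 6.0. It begins: "The analytic approach to symptoms would be similar to the approach to the condition-specific tests". For the conditions, that approach has two parts. One is a sum of Z scores, "which will constitute an improper linear model with unit weighting; this is a secondary outcome". The other is a separate analysis of each condition, restricted to patients with that diagnosis. For symptoms the plan then says: "We will set a threshold for inclusion in the composite, and use as individual dependent variables the symptoms that occur in" at least 10% of the sample.

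The next subsection adds a general commitment: "We will use separate mixed-effects models to evaluate the primary and secondary outcomes", with the baseline value as covariate and 12 months as the focus. It names a count model only for primary care use.

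**The concern.** The hypothesis is about one number per patient, and the symptom paragraph describes other quantities. It leaves five choices open:

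- whether the composite is a count or a sum of Z scores;
- which threshold admits a symptom to it, and whether that is the same 10%;
- the visit at which 10% of the sample is judged;
- whether individual symptoms are analysed in everyone or only in patients who already report them, as the diagnosis restriction in the condition-specific approach would imply;
- how error is controlled over the separate tests.

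Two things are at stake. One hypothesis may be met by any of several uncontrolled tests. The Mediation subsection could then carry a chance result forward, because it screens on outcomes that the intervention significantly affects. Also, if prevalence is judged after randomisation, a symptom that C-CHESS reduces can fall below 10% and drop out of the analysis because it improved.

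**Working it through.** **Inputs from the plan.** Two-sided alpha .05, power .80, d = .40, 100 per arm, then 132 per arm, 20% attrition and 330 recruited (section 8.0); 1:1 allocation (section 7.0). The plan gives neither the number of symptoms nor their prevalences, so those below are assumptions.

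**The plan's own figures.** n per arm = 2(1.96 + 0.84)²/0.40² ≈ 98.1, which rounds up to 99; the t-based value is 99.1. Both agree with the stated 100. Then 2 × 132 = 264, and 264/0.80 = 330, exact. The step from 100 to 132 has no formula in the plan and is taken as given. No sample size or power is stated for symptoms.

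**Multiplicity.** For k independent tests at .05, the chance of at least one false positive is 1 − 0.95^k:

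- k = 5: 0.226
- k = 10: 0.401
- k = 20: 0.642

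Positive correlation between symptoms within a patient would lower these.

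**Selection if the 10% is judged on follow-up data pooled over arms.** This used 132 per arm, binomial counts, 200,000 simulated trials and a pooled two-proportion z test. A symptom is kept if its pooled prevalence is at least 10%.

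| Control v C-CHESS | Pooled | Kept |
|---|---|---|
| 12% v 12% | 12% | 0.84 |
| 12% v 8% | 10% | 0.48 |
| 12% v 6% | 9% | 0.27 |
| 14% v 5% | 9.5% | 0.37 |

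For 14% v 5%, the chance of being both kept and significant is 0.30, against 0.73 with no selection. Reported effects are also distorted: the mean observed difference among kept symptoms is 10.6 points against a true 9, and for 12% v 6% it is 7.3 against 6. With no effect (12% v 12%), the rejection rate among kept symptoms is 0.048, so the type I error of each test is not raised.

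**Selection if the 10% is judged at baseline.** Prevalence then precedes treatment. A symptom at 12% is kept with probability 0.84 (264 patients) or 0.89 (330), and one at 14% with 0.97 or 0.99, whatever C-CHESS does later.

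**A single test of the count.** If the plan's d = .40 is taken to apply to symptoms (section 8.0 does not name them), power at 132 per arm is Φ(0.40 × √(132/2) − 1.96) = Φ(1.29) = 0.90. The pilot effect sizes for fewer symptoms are 0.45 to 0.75, from clusters of 21 to 38 patients.

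**The case against.** The strongest reply is that this is a gap in specification and not a wrong analysis. Several parts of that reply stand.

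- **The count.** A reader might infer that the number of symptoms is never tested. The documents do not support this. The count is a named measure, every secondary outcome is promised a mixed model, and the undefined composite could itself be a thresholded count. Section 6.0 also announces a list of measures and instruments that does not appear in the available text, and whether it covered symptoms cannot be told. What can be said is that no analysis of the count is specified.
- **Weighting.** A reader might infer that rare symptoms are over-weighted, since Z-scoring a yes/no item at 10% gives it 1/√(0.10 × 0.90) = 3.33 against 2.00 at 50%, a ratio of 1.67. That needs symptoms to be both yes/no and Z-scored. The plan says neither; it says only that the approach is similar. The consequence would also be small: for an assumed list of 20 symptoms, a Z-score composite of those at 10% or more correlates 0.94 to 0.98 with the raw count.
- **Power of single-symptom tests.** A reader might infer that these tests are weak throughout. At 10% v 5% and 132 per arm, power is about .34, but that is the rarest symptom eligible at baseline. The same halving from 20%, 30% or 40% gives .63, .83 and .95, before any gain from the baseline covariate and repeated measures.
- **Selection.** Dependence on treatment arises only if post-randomisation data are used. The plan does not say so, and a baseline reading is equally open. Under the adverse reading the rule works mainly against C-CHESS.

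The reply does not remove the point. The symptom-by-symptom rule, followed as stated, produces several uncontrolled tests of one hypothesis, and the text allows materially different analyses of a named secondary outcome.

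**Conclusion.** The point holds as a mismatch between the hypothesis and the specified analysis. The hypothesis concerns the number of symptoms from a list. The symptom text specifies a composite with its threshold still to be set and a test of each common symptom, with no visit fixed and no error control.

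The false-positive chance of about 23% to 64% rests on an assumed 5 to 20 independent tests and would be lower with correlated symptoms. The fall in retention from 84% to 27% rests on assumed prevalences, 132 per arm and a follow-up reading of the 10% rule; under a baseline reading it disappears. The damage in the adverse case is lost power and distorted reporting of symptoms that improved. It should not be read as a raised false-positive rate in any single test.

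This is one secondary outcome and leaves the 12-month conclusions on the primary outcomes untouched. It should still be corrected.

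**What to change.** Replace the symptom sentences in section 6.0 with two statements.

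1. The symptom outcome is the number of symptoms from the full list, in the whole sample, analysed with the planned mixed model (or its count version), with the baseline count as covariate and the 12-month contrast between arms.
2. Any symptoms reported individually are those with a baseline prevalence of 10% or more, pooled over arms, and their results are labelled descriptive or exploratory.

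If the investigators prefer to keep a composite, defining its form and threshold in advance, fixing the 10% rule at baseline and labelling the single-symptom results exploratory would close most of the gap. The count matches the hypothesis more directly.

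The cost is a short text change and fewer tests. No new data are needed, provided the symptom list is collected at each survey, as the present symptom analysis already requires. The downside is that individual symptoms would no longer support confirmatory claims.

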Participants who do not already own a computer will be receiving a laptop as part of the study. The laptop has an administration interface that allows our technical team to access devices remotely if a participant calls tech support or reports a problem. If a participant loses their laptop or installs something that is causing problems, we have the ability to remotely wipe the device, lock it down, restore the operating system and/or run a security check. We can also do security updates remotely to make sure patches are up to date on each laptop and security software has not been disabled by the user.

Patient Randomization: Once informed consent and baseline measures have been obtained from patients, they will be randomized to either the experimental (TAU + C-CHESS) or control (TAU + Internet) group, stratified on gender, clinic site, and number of chronic conditions (3-5 vs. 6+). Patients who are in the experimental group will be further randomized into two groups, one will be asked to identify a health outcome to track and share with their physician using the Clinician Report and the other group will not.

When baseline assessment and consent are complete, the researcher will enter the participant number and randomization data into a randomization spreadsheet. The interviewing researcher, once informed of group assignment, will provide setup and training.

The research staff will train participants to use C-CHESS and customize it (e.g. by health condition) during a home visit. Participants will be asked to check in regularly, initially at a daily rate with frequency of at least weekly over the course of the study.

Patient Qualitative: Data will be gathered via an interview at 3 times from 6 patients at each of the 5 clinics (N=30). Each interview is expected to take 30-60 minutes and will take place either in-person at a place of the subjects choosing or via phone.

Recruitment: Participants will be identified through a consent form opt-in question and demographics as reported on the baseline survey. We will seek a mix of genders and number of chronic conditions. We will also look at C-CHESS use data to find a mix of users and non-users. We will contact potential participants by messaging them through the C-CHESS application or phoning them.

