8.0 STATISTICAL CONSIDERATIONS

Power analyses for primary and secondary outcomes. Our power analysis was based on Elder Tree pilot data and other studies that examined the impact of behavioral interventions on single chronic conditions.⁹⁵ A meta-analysis⁹⁶ of self-management interventions found significant effects on HbA1c for diabetics ($d = .36$), and on systolic blood pressure among hypertensives ($d = -.39$). Other studies found a moderate effect size ($d = .61$) on pain behavior⁹⁷ and a small effect on number of primary care visits ($d = .28$) when patients attended self-management and peer-support meetings.^{98,99}

Because effect sizes vary for interventions of chronic conditions, we want our expected effect sizes to be conservative and yet clinically meaningful. We therefore chose an effect size of $d = .40$ for our primary

outcomes (quality of life and primary care use) as well as individual condition measures (secondary outcomes) and the composite score based on them. Adequate power ($1-\beta = .80$, two-tailed $\alpha = .05$) would require a final sample of $N=200$ patients (100 per arm).¹⁰⁰ Since we will examine 4 clusters, with 3 conditions per cluster, we will need 132 per arm. Assuming 20% attrition, we will recruit $N=330$ patients (33 per arm per clinic). This should also be sufficient for detecting similar effect sizes (at a power of $1-\beta = .80$) for condition-specific changes in diabetes,¹⁰¹ hypertension,¹⁰² and arthritis.¹⁰³ The literature is less clear in hyperlipidemia but 50% of patients are non-adherent to statins,¹⁰⁴ and statins have a high effect size,¹⁰⁵ so our goal may be achievable.

Power for mediation and moderation analyses. Power for detecting parameter changes in the structural model was estimated using a procedure of Satorra and Saris¹⁰⁶ that approximates the non-central chi-square distribution. A total N of 220 patients will provide adequate power ($> .80$) to detect a group difference in a parameter by moderate .4 standard deviations. With an N of 264 in our primary analysis, we are confident our secondary analysis will have adequate power.

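### Pooling across sites is left to a clinic-by-arm test with no stated level or consequence, and the listed model terms omit the randomisation strata

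*Combined protocol and SAP*

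**What the plan says.** Section 6.0, under the paragraph comparing TAU+Internet with TAU+C-CHESS, lists the fixed effects for every primary and secondary model: arm, time (6, 12 and 18 months) and arm-by-time, with the baseline value of the outcome as covariate. The primary focus is the arm effect at 12 months. The paragraph then says the team will determine whether clinic has a main effect or interacts with arm, and adds about the interaction: "The latter will test the consistency of C-CHESS effects over different clinics and whether data can be pooled across sites". No level, power or consequence is given for this test.

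Section 3.0 (Patient Randomization) says allocation is "stratified on gender, clinic site, and number of chronic conditions (3-5 vs. 6" or more); section 7.0 repeats the three factors. None of them is in the list of model terms. Gender and number of conditions appear in section 6.0 only as moderators.

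Two other places presuppose a single pooled analysis. Section 6.0 (Quantitative analyses) describes the analysis of quality of life and primary care use as whole-sample. Section 8.0 sizes the trial on the pooled arms ("we will need 132 per arm") and refers to 264 patients in the primary analysis.

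**The concern.** A check that effects are consistent across centres is ordinary practice. This sentence goes further, because it makes pooling something the trial's own data will decide. Pooled analysis is what the sample size rests on, so the primary analysis carries a condition whose trigger and alternative are both unstated. If the test is not significant, a reader may take that as evidence of consistency, which a test this size cannot give. If it is significant, nobody knows from the plan what the primary result is, and the choice would be made after seeing the data.

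Separately, clinic would be examined for a main effect rather than included by design, which is a second data-dependent choice. Stratified allocation balances the three factors between arms. A linear model that leaves them out keeps their variance in the error term and gives standard errors larger than they need be.

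**Working it through.** **Inputs from the documents.** Section 8.0: d = .40, two-sided alpha .05, power .80, 100 per arm, then 132 per arm, 20% attrition, 330 recruited, "33 per arm per clinic". Number of clinics: 330 / (2 × 33) = 5, which agrees with the five clinics in section 3.0 (Patient Qualitative).

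**Assumptions.** Equal clinic sizes, outcome SD 1, a continuous outcome at the single 12-month contrast, and alpha .05 for the interaction test.

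**The plan's own figures.** The two-sample formula at d = .40 gives 99 per arm, against 100 stated; t-based power at 100 per arm is .804. Recruitment is 264 / .8 = 330. Both reproduce. (The step from 100 to 132 per arm has no stated formula; nothing here depends on it.) At 132 per arm, power for d = .40 is .90.

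**Evaluable patients per clinic.** 33 × .8 = 26.4 per arm.

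**Power of the interaction test.** Noncentral F with 4 and 250 df, 26 per arm per clinic, noncentrality = 4 × SD² / (2/26), where SD is the spread of true clinic effects:

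- SD .1: noncentrality .52, power .08
- SD .2: noncentrality 2.08, power .17
- SD .3: noncentrality 4.68, power .37

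Specific patterns with mean effect .40, at 26.4 per arm per clinic:

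- effects evenly spaced from .2 to .6: .12
- one clinic at 0 and four at .5: .21
- evenly spaced from 0 to .8: .41

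Power reaches .80 only when effects run from about −.2 to 1.0. If baseline adjustment reduces the SD (assumed correlation .5 to .7), the three patterns become .15 to .21, .28 to .40 and .53 to .72.

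**What happens if the test is acted on when the effect is the same everywhere.** It rejects with probability .05 per outcome, and 1 − .95² = .0975 for at least one of two primary outcomes if they are independent. With balanced normal data the pooled estimate is independent of the interaction statistic, so for each outcome:

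- No efficacy claim after rejection: power .95 × .90 = .856; type I error .95 × .05 = .0475.
- By-clinic claims after rejection, Bonferroni over five clinics: simulated type I error about .07, power .903.
- By-clinic claims after rejection, any clinic at .05: simulated type I error .095, power .907.

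The excess type I error arises because a trial that rejects homogeneity nearly always contains an extreme clinic: .0475 + .05 × .95 = .095.

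**Precision.** The 95% half-width is 1.96 × √(2/132) = .24 SD pooled and 1.96 × √(2/26.4) = .54 SD in one clinic. Under a common effect of .40 the chance that at least one clinic estimate is negative is about .32, so apparent inconsistency should be expected.

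**The case against.** The strongest reply is that no split analysis is planned. The whole-sample description and the 264 patients point to a pooled intent, and the sentence may be a loosely worded consistency check. That stands in part: a reader might infer that the primary analysis will be run clinic by clinic, but the documents never say so. What they leave open is the consequence of a significant test.

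A reader might also infer that low power makes the test likely to split the analysis wrongly. That is backwards. Low power leads to pooling when effects differ; wrong splitting comes only from type I error, 5% per outcome.

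Nor should single-clinic power (about .29 at 26 per arm) be set against .90 as the cost. That branch is reached about 5% of the time under a common effect, and the loss in overall power is at most about 4 points. The .0975 is the chance of triggering the test on at least one primary outcome, not of a false efficacy claim.

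The word for sites is ambiguous too. Section 5.0 applies it to the two institutions. If pooling means UW versus MUSC, the test has 1 df. With an assumed equal split of 66 per arm, its power is .37 for a difference in effect of .4 and .90 for a difference of .8. The numbers change, but the missing consequence does not.

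Finally, the benefit of covariate adjustment cannot be sized from the documents, since it depends on how prognostic the strata are once baseline is in the model. It also need not carry over to the logistic fallback for primary care use, where adjustment does not generally shrink standard errors. Both limits stand.

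**Conclusion.** The point holds as a gap in specification with a modest statistical cost. Section 6.0 makes pooling depend on a test without a level or a consequence, while sections 6.0 and 8.0 elsewhere assume one whole-sample analysis, and the listed model terms leave out the factors used to randomise.

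The test misses moderate heterogeneity most of the time (power .17 to .37), so it cannot certify consistency. If it were acted on after a chance rejection, overall power would fall from .90 to about .86, or type I error would rise to between about .07 and .095, depending on a rule the plan does not give. These figures rest on five equal clinics, SD 1, alpha .05 and a continuous outcome at 12 months. More clinics (section 3.0 allows at least five for clinician recruitment) would make each one smaller. The documents do not support saying that a by-clinic primary analysis is planned, or that the trial would lack a valid result.

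**What to change.** In section 6.0:

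- State that the pooled 12-month arm effect is the primary result whatever the clinic-by-arm test shows.
- Include clinic, gender and condition-count stratum (3-5 vs 6+) as fixed covariates in every primary and secondary model, regardless of their p-values.
- Report clinic-by-arm estimates with confidence intervals as a descriptive consistency check, and say whether the unit is the clinic or the institution.
- Delete the closing clause of the quoted sentence, on pooling across sites.

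The cost is one paragraph of text and, with five clinics, 4 + 1 + 1 = 6 degrees of freedom out of 264 patients. Sample size and trial conduct do not change, and the consistency check is kept.
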